7.1.3 Endpoint

The objective of the study is to analyze the performance of FIT, miR-92a and their combination for the detection of AN, evaluating performance indicators such as sensitivity, specificity, predictive values, diagnostic accuracy, likelihood ratios, and overall compliance rate, to formulate a strategy for early screening and prevention of CRC for an average-risk population. Once the project is initiated, the researchers will monitor the progress of enrolment, results of miR-92a and FIT, and colonoscopy and pathology results in real time, and will determine whether to terminate enrolment early based on the number of enrolments and fecal-based miR-92a positivity rate.

Data summaries for all subjects will be summarized in a frequency table:

	Colonoscopy	and/or histopatholog	T. 4-1	
Test result	CRC	AA	NEG	Total
Positive	a	b	c	a+b+c
Negative	d	e	f	d + e + f
Total	a + d	b + e	c + f	N

CRC colorectal cancer, AA advanced adenomas, NEG negative (including polyps, other non-colorectal cancerous lesion and no findings)

- (1) The sensitivity and specificity will be calculated as:
- xx test sensitivity for subjects with CRC = a/(a + d)
- xx test sensitivity for subjects with AA = b/(b + e)
- xx test sensitivity for subjects with AN = (a + b)/(d + e)
- xx test specificity for subjects with negative findings = f/(c + f)
- (2) The PPV and NPV will be calculated as:
- PPV (CRC) = Probability of having CRC given a positive xx test result = a/(a + b + c)
- PPV (AA) = Probability of having AA given a positive xx test result = b/(a + b + c)
- PPV (AN) = Probability of having AN given a positive xx test result = (a + b)/(a + b + c)
- NPV = Probability of having negative findings on colonoscopy given a negative xx test result = f/(d + e + f)
- (3) The LRs will be calculated as:
- PLR (CRC) = P (Test positive | CRC)/P (test positive | No CRC) = a/(b+c)
- PLR (AA) = P (Test positive | AA)/P (test positive | No AA) = b/(a + c)
- PLR (AN) = P (Test positive | AA or CRC)/P (test positive | No AA nor CRC) = (a + b)/c
- NLR (NEG) = P (Test negative | NEG)/P (test negative | AA or CRC) = f/(d + e)

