1.4 Study population

This is a prospective study of a population at average risk for CRC. 16,505 subjects aged from 30 to 75 will be enrolled in this prospective study based on inclusion and exclusion criteria, if they are fully informed about the study and sign the informed consent. The investigators will continue to monitor the progress of enrolment and the rate of positivity for miR-92a, after the start of the study to determine whether enrolment should be terminated early.

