5.1 Enrolment of subjects

The target population for this study was the average risk group for CRC aged 30 – 75 years. Subjects will be recruited based on the inclusion and exclusion criteria. Subjects will be excluded if they are recruited but meet the exclusion criteria. The target population is divided into age groups of 5 years. Laboratory testing will be initiated as soon as the subject has been successfully recruited and has provided a satisfactory stool sample. The researchers will monitor the progress of the subjects and the results of the laboratory tests in real time and will count the number of enrolments and fecal-based miR-92a positivity in time to determine whether to terminate the enrolment early.

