5.5 Sample size considerations

The required sample size for the test is based on the following assumptions:

The ratio of AA to CRC in general risk population is 10:1;

Among the population aged 30 - 75, approximately 30 out of every 10,000 people are patients with CRC and 300 out of every 10,000 people are patients with AA;

The sensitivity and specificity of fecal-based miR-92a detection for CRC are 90% and 90%, respectively. The sensitivity and specificity of fecal-based miR-92a detection for AA are 80% and 90%, respectively;

The sample dropout rate is 5%.

According to the Buderer formula [13], the required sample size is estimated as follows:

Step1: Specifications

SN: sensitivity; SP: specificity; 1- α : confidence level; $Z_{1-\alpha/2}$: standard normal deviation (when $\alpha = 0.05$, $Z_{1-\alpha/2} = 1.96$); W: allowable error, set to 0.09 here; Prevalence: prevalence rate, which is the ratio of positive cases in all samples. We set the prevalence rate for CRC to be 0.3% and the prevalence rate for AA to be 3%.

Step2: Calculate the number with disease, TP + FN

TP + FN =
$$Z_{1-\alpha/2}^2 \frac{SN(1-SN)}{W^2}$$

Step3: Calculate the sample size required for sensitivity, N₁

$$N_1 = \frac{TP + FN}{P}$$

For CRC, $N_1 = 14,228$; for AA, $N_1' = 2,529$

Step4: Calculate the number without disease

$$FP + TN = Z_{1-\alpha/2}^{2} \frac{SP(1 - SP)}{W^{2}}$$

Step5: Calculate the sample size required for specificity, N2

$$N_2 = \frac{FP + TN}{1 - P}$$

For CRC, $N_2 = 43$; for AA, $N_2' = 78$

Step6: Select the final sample size, N

$$N = 14,228$$

In summary, considering a 5% dropout rate, the required sample size is 14,975. To ensure sufficient sample size after excluding unqualified samples, 15,586 individuals were ultimately included in this study.

6. Research program design and processes

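### Enrolment may close early on the miR-92a positivity rate, a very weak guide to the number of cancers that sets the sample size, and no minimum number enrolled is stated

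*Protocol*

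**What the plan says.** Three sections of the protocol allow enrolment to end early, on two quantities.

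- Section 1.4 has the investigators follow enrolment progress and "the rate of positivity for miR-92a, after the start of the study to determine whether enrolment should be terminated early".
- Section 5.1 has them "count the number of enrolments and fecal-based miR-92a positivity in time to determine whether to terminate the enrolment early".
- Section 7.1.3 says they "will determine whether to terminate enrolment early based on the number of enrolments and fecal-based miR-92a positivity rate". It adds that miR-92a, FIT, colonoscopy and pathology results are all followed in real time.

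No section states a positivity value that would trigger closure, whether a high or a low rate would do so, or a number below which enrolment may not close.

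Section 5.5 derives the size from the precision of sensitivity: "W: allowable error, set to 0.09 here". The CRC calculation governs, giving 14,228 subjects (2,529 for advanced adenomas, AA) and 14,975 after a 5% dropout allowance.

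**The concern.** A rule for closing enrolment should show whether the study has what its sample size was meant to deliver. Here that is a number of cancers. The number enrolled bears on it only through the assumed 0.3% prevalence, and no floor is attached. The other criterion, the positivity rate of the index test, is made up mainly of people without CRC or AA.

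Two things are at stake. Enrolment could close with too few cancers for the stated precision. And because the rate moves mainly with the false-positive fraction, closing on it means closing partly on the specificity that the study sets out to estimate.

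**Working it through.** **Inputs, all from section 5.5.** z = 1.96; W = 0.09; CRC prevalence 0.3%; AA prevalence 3% (a 10:1 ratio). Assumed miR-92a performance: SN 90% in CRC and 80% in AA, SP 90% for both. Dropout 5%.

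**1. The plan's own figure.** Cases needed = z² × SN(1−SN)/W².
- CRC: 3.8416 × 0.09/0.0081 = 42.7 cases; 42.68/0.003 = 14,228. This reproduces.
- AA: 3.8416 × 0.16/0.0081 = 75.9 cases; 75.88/0.03 = 2,529. This reproduces.
- Dropout: 14,228/0.95 = 14,977, against 14,975 stated; the difference of 2 is immaterial.

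**2. Expected positivity.** Rate = 0.9 × pCRC + 0.8 × pAA + (1−SP) × (1 − pCRC − pAA).

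| Source | Calculation | Points | Share of positives |
|---|---|---|---|
| CRC | 0.9 × 0.003 | 0.27 | 2.2% |
| AA | 0.8 × 0.03 | 2.40 | 19.4% |
| False positives | 0.1 × 0.967 | 9.67 | 78.4% |
| Total | | 12.34 | 100% |

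**3. Sampling error of the rate.** √(0.1234 × 0.8766/N) is 0.28 points at N = 14,228 and 0.38 points at N = 7,500.

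**4. CRC prevalence halved, AA unchanged.** 0.00135 + 0.024 + 0.1 × 0.9685 = 12.22%, a fall of 0.12 points. Expected cancers at 14,228 fall from 42.7 to 21.3. The shift is under half a standard error at 14,228 and under a third at 7,500.

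**5. CRC and AA both halved, keeping 10:1.** 0.00135 + 0.012 + 0.1 × 0.9835 = 11.17%, a fall of 1.17 points, or about 4 standard errors at 14,228 and 3 at 7,500. This would be visible if specificity were known to be 90%. To bring the rate back to 12.34%, the false-positive fraction must be (0.1234 − 0.01335)/0.9835 = 0.1119, that is, a specificity of 88.8%. A change of 1.2 points in specificity hides the loss of half the cancers and half the adenomas.

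**6. What the rate does track.** One point of specificity moves it by 0.967 points. At fixed N, the number of positives explains about 1.7% of the variance in the number of cancers: r = 0.003 × (0.9 − 0.1234)/√(0.003 × 0.997 × 0.1234 × 0.8766) = 0.13. For the number of false positives the figure is about 76%: 0.0967 × 0.8766/(0.9033 × 0.1234).

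**7. Cost of stopping short.** Half-width = 1.96 × √(0.09/cases), at 0.3% prevalence. The stopping points are illustrations, because the protocol names none.

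| Subjects | Expected CRC | Half-width, points |
|---|---|---|
| 5,000 | 15 | 15.2 |
| 7,500 | 22.5 | 12.4 |
| 10,000 | 30 | 10.7 |
| 12,000 | 36 | 9.8 |
| 14,228 | 42.7 | 9.0 |

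These are cancers present among the subjects. Only test-positives and a sample of negatives go to colonoscopy (sections 2.3 and 6.6), so fewer would be confirmed.

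**The case against.** The strongest reply is that the number enrolled is also a criterion, and multiplied by 0.3% it gives the expected cancers directly. That is correct, and the rule cannot be described as resting on positivity alone. But no minimum is attached to that number, and 0.3% is the assumption that monitoring ought to guard against.

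The stated main objective is advanced neoplasia (sections 7.1.1 and 7.1.3), and AA needs only 2,529 subjects. An early stop would harm that estimate much less than CRC sensitivity. This stands, but CRC sensitivity is what section 5.5 used to set the size.

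Several stronger readings are tempting and are not supported:

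- *The rate carries no information about cancers.* It carries a little: about 1.7% of the variance at fixed N, and more if the 10:1 ratio and the 90% specificity are taken as known.
- *Unblinded researchers can stop at a favourable moment and so bias the accuracy estimates.* Section 7.1.3 describes real-time monitoring, but the stopping basis that it states does not use the colonoscopy results. The protocol is silent on blinding, and no size of bias can be derived from it.
- *The clause led to a study that was too small.* Section 2.3 reports 16,505 enrolled and section 5.5 reports 15,586 included, both above 14,975.

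An analysis plan that is not shown could add detail. It would not cure the choice of criterion, which the protocol itself makes in three places.

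**Conclusion.** The point holds as a mismatch between the stopping criteria and the sample-size rationale. Positivity is a very weak proxy for the CRC count and is confounded with specificity. Neither it nor the number enrolled, as worded, protects the ±9-point target. The possible loss depends on where enrolment would close; at 7,500 subjects the half-width would be 12.4 points. Selection on apparent specificity is a possibility that the wording leaves open; its direction and size cannot be stated, because the protocol gives no threshold or direction. All figures rest on the planning values of section 5.5, and the early stopping points are illustrative.

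**What to change.** In sections 1.4, 5.1 and 7.1.3, delete the miR-92a positivity rate as a ground for early termination. Then state one of two rules: enrolment runs to the planned number, or it may not close before the 14,975 required by section 5.5 are enrolled. In either case, state that the decision is made without reference to test-specific results. If the first rule is chosen, name the number, since sections 1.4 and 2.3 give 16,505 enrolled and section 5.5 gives 15,586 included.

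Closing when 43 confirmed CRCs are reached is less suitable. Suppose negatives are sampled one for one with miR-92a positives. Of 42.7 cancers at 14,228, the test would find 0.9 × 42.7 = 38.4, and sampling about 14% of negatives (0.1234/0.8766) would add about 0.6. About 39 would be confirmed even with full uptake (FIT ignored, as no FIT sensitivity is given). Such a count would rarely reach 43 before full size, and it depends on the sensitivity of the test.

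The change is one of wording; the cost is less freedom to stop early. A floor secures the expected number of cancers, not the actual one: at 14,228 subjects and 0.3% prevalence, the chance of 43 or more is about 50%.

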7.1 Test termination points

7.1.1 Relevant definitions

The main objective of the study was to examine the performance of FIT, miR-92a, and FIT + miR-92a for AN. Colonoscopy and histopathology were used as the gold standard to determine the classification of the subject.

Sayooning toot	Colonoscopy and histopathology		
Screening test	Patients	Nonpatients	
Positive	True positive (TP)	False positive (FP)	
Negative	False negative (FN)	True negative (TN)	

When counting the performance of different screening protocols for CRC, subjects with a positive screening test result and a confirmed colonoscopy diagnosis of CRC were counted as true positives, otherwise they were counted as false positives, and subjects with a negative screening test and a confirmed colonoscopy diagnosis of a non-colorectal cancerous lesion, such as a normal, inflamed, polyps, advanced adenoma, or other non-colorectal cancerous lesion were counted as true negatives, otherwise they were counted as false negatives.

When counting the performance of different screening protocols for AN (CRC and AA), a positive screening test with a confirmed colonoscopy diagnosis of CRC or AA was counted as a true positive, otherwise it was counted as a

false positive, and a negative screening test with a confirmed colonoscopy diagnosis of a normal, inflamed, polyps, or other non-colorectal cancerous lesion was counted as a true negative, otherwise it was counted as a false negative.

Specific screening and analysis performance indicators are calculated as follows:

- Sensitivity (SN): also known as true positive rate (TPR), defined as true positive/ (true positive + false negative) × 100%;
- Specificity (SP): also known as true negative rate (TNR), defined as true negative/ (true negative + false positive) × 100%;
- Accuracy (ACC): defined as (true positive + true negative)/ (positive + negative) × 100%;
- Positive predictive value (PPV): defined as true positive/ (true positive + false positive) × 100%;
- Negative predictive value (NPV): defined as true negative/ (true negative + false negative) ×100%.

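### The printed formula for sensitivity for advanced neoplasia divides by the false negatives only, so it yields an odds, not a sensitivity

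*Protocol*

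**What the plan says.** Section 7.1.1 of the protocol names AN as the main target: "The main objective of the study was to examine the performance of FIT, miR-92a, and FIT + miR-92a for AN". The same section gives the general rule, "Sensitivity (SN): also known as true positive rate (TPR), defined as true positive/ (true positive + false negative", and says what counts as a true positive for AN: "a positive screening test with a confirmed colonoscopy diagnosis of CRC or AA was counted as a true positive".

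Section 7.1.3 then sets out a frequency table with cells a to f and states formulas in those letters. For the two components of AN it has "xx test sensitivity for subjects with CRC = a/(a + d" and "xx test sensitivity for subjects with AA = b/(b + e", which are a/(a + d) and b/(b + e). For AN itself it has "xx test sensitivity for subjects with AN = (a + b)/(d + e", which is (a + b)/(d + e).

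The meaning of d, e and f is confirmed by the negative predictive value line, "NPV = Probability of having negative findings on colonoscopy given a negative xx test result = f/(d + e + f". Its denominator is all test-negative subjects, so d and e are the test-negative CRC and AA cases.

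Section 7.2 lists sensitivity for AN among the main indicators. Section 7.4 plans to report sensitivity as a binomial proportion with an exact 95% interval.

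**The concern.** A sensitivity needs all diseased subjects in its denominator. The AN line leaves out the detected cases, a + b, and keeps only the missed ones, d + e. The result is a ratio of detected to missed cases, which has no upper limit of 100%.

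Two things are at stake. If true sensitivity is above 50%, the result is visibly impossible, and no exact binomial interval can be formed because the numerator exceeds the denominator. If true sensitivity is below 50%, the result is wrong but under 100%, and nothing in the output warns the reader. The line is a calculation rule in the section headed Endpoint, stated for a generic test, so it would be applied to FIT, miR-92a and their combination alike.

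**Working it through.** **Inputs.**
- Section 5.5 (planning values for miR-92a): CRC in 30 and AA in 300 of every 10,000 people; sensitivity 90% for CRC and 80% for AA; allowable error W = 0.09; z = 1.96.
- Section 7.1.3: cell letters and the printed formula.
- Section 7.1.1: definition of sensitivity.

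**Step 1. Reproduce the plan's own figures, to confirm the inputs.** N1 = z² × SN(1 − SN)/W²/prevalence.
- CRC: 1.96² × 0.9 × 0.1/0.09² = 42.68 diseased; 42.68/0.003 = 14,228, as stated.
- AA: 1.96² × 0.8 × 0.2/0.09² = 75.88 diseased; 75.88/0.03 = 2,529, as stated.

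**Step 2. Fill the AN cells per 10,000 people.**

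| | CRC | AA | AN |
|---|---|---|---|
| Test positive | a = 30 × 0.9 = 27 | b = 300 × 0.8 = 240 | 267 |
| Test negative | d = 30 − 27 = 3 | e = 300 − 240 = 60 | 63 |
| Total | 30 | 300 | 330 |

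**Step 3. Apply each formula.**
- CRC line: a/(a + d) = 27/30 = 90%. AA line: b/(b + e) = 240/300 = 80%. Both return their inputs.
- Printed AN line: (a + b)/(d + e) = 267/63 = 4.238, or 424%.
- Definition in section 7.1.1, with TP = a + b and FN = d + e: 267/(267 + 63) = 267/330 = 80.9%.

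Pooled sensitivity is a weighted average of the CRC and AA values, so it must lie between 80% and 90%. The 80.9% does; the 424% does not.

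**Step 4. General form.** With D diseased subjects and sensitivity Se, a + b = D × Se and d + e = D × (1 − Se). The printed line is therefore Se/(1 − Se).

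| True sensitivity | Printed line gives |
|---|---|
| 30% | 0.3/0.7 = 42.9% |
| 40% | 0.4/0.6 = 66.7% |
| 50% | 0.5/0.5 = 100% |
| 60% | 0.6/0.4 = 150% |
| 80% | 0.8/0.2 = 400% |
| 90% | 0.9/0.1 = 900% |

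The printed value is too high at every sensitivity above zero, and it passes 100% once true sensitivity passes 50%.

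**The case against.** The best defence is that the intended quantity is not in doubt. Section 7.1.1 defines sensitivity correctly and assigns true positives and false negatives for AN specifically. The binomial interval of section 7.4 only makes sense for the section 7.1.1 form. On this view a term was dropped from one line, and the design is sound. That is fair, and it is why the remedy is small. It does not excuse the line: section 7.1.3 is where the calculation is written out cell by cell, so a programmer may well work from it.

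A term could also have been lost when the text was read from PDF. This cannot be fully excluded, but the line is complete and well formed, and its two neighbours are intact.

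Three stronger readings are tempting, and the protocol does not support them.
- A reader might infer that every test would show an impossible value. That holds only where true sensitivity is above 50%. Section 5.5 gives planning sensitivities for miR-92a alone, none for FIT or the combination.
- A reader might infer a far larger distortion among subjects who actually have colonoscopy, because only some test-negative subjects are examined. Any such figure needs an assumed fraction of negatives examined, which the protocol does not state. Section 6.6.2 describes three separate draws of negatives, and sections 2.3 and 6.6 also send FIT-positive subjects who are miR-92a-negative to colonoscopy. A calculation from a single draw with full uptake does not represent this design.
- A reader might conclude that the formula must also be weighted for partial verification. That is a separate methodological question. The denominator error exists without it and is cured without it.

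**Conclusion.** The AN sensitivity line in section 7.1.3 is wrong as written. It is the odds Se/(1 − Se), and it contradicts both section 7.1.1 and the CRC and AA lines beside it.

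For miR-92a at the planning assumptions (prevalence 0.3% and 3%, sensitivity 90% and 80%), it gives 424% where the sensitivity is 80.9%. The algebra does not depend on those assumptions; only the size of the discrepancy does.

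The reach is limited. The sample size in section 5.5 uses the CRC and AA sensitivities separately and does not change. The specificity and predictive value lines do not use this expression. The fault nevertheless lies in a main indicator for the study's main target, so it should be corrected before the formula is used.

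**What to change.** In section 7.1.3, replace the AN line with: sensitivity (AN) = (a + b)/(a + b + d + e). The denominator is then the sum of the CRC and AA column totals in the section's own table, in agreement with section 7.1.1, and the binomial proportion and exact 95% interval of section 7.4 apply directly.

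The cost is one line of text. No change to design, data collection or sample size follows. Any analysis code already written from section 7.1.3 should be checked for the same denominator.

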2.3 Research content

The study was conducted at Shenzhen People's Hospital (SZH) (head unit), Shenzhen Bao'an District Hospital of Traditional Chinese Medicine (BAT) and Tianjin Nankai Hospital (NKH). 16,505 subjects were enrolled according to the inclusion and exclusion criteria. During the recruitment process, the researchers will fully introduce the content, risks and value of the study to the subjects. Subjects will sign an informed consent to participate in the study after they have been fully informed of the content, risks and benefits of the study and their questions have been answered. A short interview using the CRC risk questionnaire will be conducted and a stool sample collection kit will be given to the subjects. One stool sample will be collected according to the stool sample collection instructions and returned to the clinical site. The sample will be used for fecal-based miR-92a and FIT (9. Instructions for stool sample collection). Colonoscopy and/or pathology will be performed on subjects with positive fecal-based miR-92a and/or FIT. Some screen-negative individuals will also be randomly selected for colonoscopy and/or pathological examination. The study will analyze the performance of FIT, miR-92a and their combination in the screening of CRC and AA [advanced neoplasia (AN)] using colonoscopy and/or pathological findings as the gold standard.

3. Research target

To analyze the performance of FIT and fecal-based miR-92a and their combination for AN, and to evaluate the performance indicators and form an early screening and prevention strategy for people at average risk of CRC.

4. Research methods

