6.6.2 Subjects tested negative for fecal samples

The researchers actively followed up with randomly selected subjects under the following three conditions and provided education on bowel health and bowel cancer prevention while promoting timely completion of colonoscopies:

- A comparable number of fecal miR-92a-positive subjects were randomly chosen from among the fecal miR-92a-negative subjects.
- A comparable number of FIT-positive subjects were randomly chosen from among the FIT-negative subjects.
- A comparable number of fecal miR-92a & FIT-positive subjects were randomly chosen from among the fecal miR-92a & FIT-negative subjects.

Random method: Develop a Microsoft Excel worksheet to systematically categorize and enumerate all fecal test-negative subjects who have successfully undergone fecal sample testing but have not been randomized. Specifically, segregate the subjects into three distinct groups: those who tested negative for fecal miR-92a, those who tested negative for FIT, and those who tested negative for both fecal miR-92a and FIT. Number each subject within their respective group, and categorize them further based on age groups, with a distinct consideration for gender. Populate column A with the sequential subject numbers for each age-gender group. Utilize the Random function in column B, executing the command by pressing the Enter key, and subsequently generate the data columns by dragging down the cells. Select the

corresponding subject numbers for follow-up in ascending order to ensure a systematic and unbiased approach for further analysis.

Random example: A cohort of 200 subjects, who had undergone stool sample testing but had not been randomized, comprised the study population. This group included 120 males and 80 females. Notably, within the 51 – 55 age bracket of male subjects, 40 individuals were evaluated, among whom 3 tested positives for miR-92a. Subsequently, the researchers adopted a randomized approach to select 3 of the remaining 37 male subjects within this age group, who had negative miR-92a test results, for active follow-up and colonoscopy. The methodology employed for this selection and subsequent colonoscopy procedure is outlined below.

- Create a new Microsoft Excel worksheet and enter the subject numbers of fecal miR-92a test-negative male subjects in the 51-55 age group in column A, e.g., SZH00051-SZH00087.
- In cell B1 enter the function: = RAND ().

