- After clicking on the model to execute the function, drop down the cell and generate random data.
- Select the data cells in column B, right-click the mouse and select "Sort" in the "ascending".
- By expanding the selected region, the data in column A can be redistributed randomly.
- Select the first three rows of the worksheet, select the toolbar in the "data" menu in the "combination" option, read
 the number obtained that is randomly selected subjects.
- Initiate a follow-up telephone call with three randomly selected subjects to follow up on the completion of the colonoscopy. If any of the subjects refused to undergo colonoscopy, the randomized follow-up subjects were deferred.

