7.4 Statistical methods

A variety of categorical data analysis methods will be used to analyze the results from the miR-92a, FIT and FIT + miR-92a results. Binomial proportions and exact 95% CI summarize sensitivity and specificity across categories. According to the study design, FIT and miR-92a from the same subjects were considered as a paired design, and the exact McNemar's test was used to compare the differences of DR, PR, Se and Sp between these two groups. Given the susceptibility of PPV to confounding factors like prevalence and subject characteristics, the GEE (Generalized Estimating Equations), which is based on McNemar's test, was utilized to compare the differences in PPV between the two groups.

8. Ethical issues

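### Sensitivity, specificity, accuracy and NPV are fixed as raw proportions of colonoscoped subjects, although negatives are scoped at a far lower rate than positives; specificity is understated and AN/AA sensitivity overstated

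*Protocol*

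**What the plan says.** **Who is scoped.** Protocol 2.3: "Colonoscopy and/or pathology will be performed on subjects with positive fecal-based miR-92a and/or FIT". For the rest: "Some screen-negative individuals will also be randomly selected for colonoscopy and/or pathological examination".

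**How many negatives.** Section 6.6.2 sets three draws, matched in number to the miR-92a positives, to the FIT positives, and to the subjects positive on miR-92a and FIT. The first reads: "A comparable number of fecal miR-92a-positive subjects were randomly chosen from among the fecal miR-92a-negative subjects". Draws are made within age-sex groups. In the worked example, with 3 positives among 40 men, "the researchers adopted a randomized approach to select 3 of the remaining 37 male subjects within this age group". That is 3/3 = 100% of positives and 3/37 = 8.1% of negatives. On refusal: "If any of the subjects refused to undergo colonoscopy, the randomized follow-up subjects were deferred".

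**How performance is computed.** Section 7.1.1 defines sensitivity, specificity, accuracy, PPV and NPV from simple counts. Section 7.1.3 repeats this from a table with cells a to f: "xx test sensitivity for subjects with CRC = a/(a + d" and "xx test specificity for subjects with negative findings = f/(c + f". Section 7.4 adds: "Binomial proportions and exact 95% CI summarize sensitivity and specificity across categories".

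The protocol mentions no sampling fraction, weight or partial-verification correction.

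**The concern.** Colonoscopy with histology is the only reference standard, so a subject who is not scoped cannot enter cells a to f, even though 7.1.3 introduces the table as covering everyone. The positive row (a, b, c) is close to complete, while the negative row (d, e, f) is a thin sample. Sensitivity, specificity and accuracy divide across the two rows, so missing negatives remove false negatives from one denominator and true negatives from the other. This is partial-verification bias, and it affects what 7.2 calls the main indicators.

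Single-test NPV is affected by another route. Subjects negative on one test but positive on the other are all scoped, so they are over-represented among that test's scoped negatives. Matching within age-sex groups adds a further departure from simple random sampling.

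At stake is whether the published figures describe an average-risk population, which is the aim in 1.3.

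**Working it through.** **1. The plan's own figure (5.5).** CRC: 1.96² × 0.90 × 0.10 / 0.09² = 42.68 cases; 42.68/0.003 = 14,228, as stated. AA: 1.96² × 0.80 × 0.20 / 0.09² / 0.03 = 2,529, as stated. With 5% dropout, 14,228/0.95 = 14,977 (stated 14,975). The calculation treats every subject's disease status as known.

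**2. Expected full table for miR-92a.** Inputs from 5.5: CRC 0.3%, AA 3%, sensitivity 0.90 and 0.80, specificity 0.90, N = 14,228.

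| | CRC | AA | NEG | Total |
|---|---|---|---|---|
| Positive | 38.4 | 341.5 | 1,375.8 | 1,755.7 |
| Negative | 4.27 | 85.4 | 12,382.6 | 12,472.3 |

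AN sensitivity here is TP/(TP+FN) as in 7.1.1. The 7.1.3 expression (a+b)/(d+e) omits the true positives from the denominator and is a separate error.

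**3. Upper case: miR-92a alone, one 1:1 draw, full attendance.** Fraction of negatives scoped: 1,755.7/12,472.3 = 0.141. Scoped negatives: d = 0.60, e = 12.0, f = 1,743.

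- Specificity: 1,743/(1,743 + 1,375.8) = 0.559 (true 0.900); exact CI 0.541-0.576.
- AN sensitivity: 379.9/(379.9 + 12.6) = 0.968 (true 0.809); exact CI 0.944-0.982.
- AA sensitivity: 0.966 (true 0.800). Accuracy: 0.605 (true 0.897).
- CRC sensitivity: 0.985 (true 0.900). With 38 of 39 cases positive, the exact CI is 0.865-0.999, which contains 0.90.

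**4. The three-draw design of 6.6.2.** FIT performance is not in the protocol. One assumed scenario: FIT sensitivity 0.70 for CRC and 0.25 for AA, specificity 0.95, tests independent given disease status.

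- FIT positives: 14,228 × (0.003×0.70 + 0.03×0.25 + 0.967×0.05) = 824.5; FIT negatives 13,403.5.
- Positive on both: 181.1. Negative on both: 11,828.8 (CRC 1.3, AA 64.0, NEG 11,763.5).
- Double-negatives scoped: 1 − (1 − 1,755.7/12,472.3)(1 − 824.5/13,403.5)(1 − 181.1/11,828.8) = 0.206. All others are scoped.
- miR-92a specificity: scoped true negatives are 0.206 × 11,763.5 + 619.1 (FIT-positive) = 3,042.0; 3,042.0/(3,042.0 + 1,375.8) = 0.689 (true 0.900).
- miR-92a AN sensitivity: scoped false negatives are 0.206 × 65.3 + 24.3 = 37.8; 379.9/417.7 = 0.910 (true 0.809).
- miR-92a accuracy: (379.9 + 3,042.0)/4,835.5 = 0.708 (true 0.897).
- miR-92a CRC sensitivity: 0.922 (true 0.900).
- Combination: specificity 2,422.9/(2,422.9 + 1,994.9) = 0.548 (true 0.855); AN sensitivity 0.968 (true 0.861).
- FIT NPV: 0.930 (true 0.975).

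**5. Range.** FIT CRC sensitivity 50-80%, AA sensitivity 10-30%, specificity 90-95%. The third draw can be read as matching subjects positive on both tests or on either.

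| | Third draw: both | Third draw: either | True |
|---|---|---|---|
| miR-92a specificity | 0.68-0.75 | 0.78-0.82 | 0.90 |
| miR-92a AN sensitivity | 0.89-0.94 | 0.87-0.91 | 0.81 |
| Combination specificity | 0.52-0.55 | 0.65-0.68 | 0.81-0.86 |
| Combination AN sensitivity | 0.95-0.97 | 0.92-0.95 | 0.83-0.87 |

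**6. Weighting recovers the truth.** In step 4, dividing the scoped double-negatives by 0.206 restores 12,382.6/13,758.4 = 0.900 and 379.9/(379.9 + 89.7) = 0.809.

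**7. Its price for CRC (one-test case).** The weighted count of missed cancers has variance about 0.60/0.141² ≈ 30. By the delta method, SE ≈ √[(38.4/42.7²)² × 30 + (4.27/42.7²)² × 38.4] ≈ 0.117, a half-width of about 0.23 against the planned 0.09. The chance of no missed cancer among the scoped negatives is about e^(−0.60) = 0.55.

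**The case against.** Several stronger readings are tempting, and the documents do not support them.

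- **That the study cannot answer its question.** The negatives are drawn at random within known groups, so the fault lies in the estimator and can be repaired. PPV, and McNemar tests resting on discordant pairs, need no scoped double-negatives and stand if positives attend. The estimated differences in sensitivity and specificity still need correcting, because their denominators are affected.
- **That every exact interval misses the truth.** This fails for CRC sensitivity, the quantity that sets N. Its interval contains 0.90 even at 38/39, and once FIT-triggered colonoscopies are counted its bias is only about 0.01-0.04.
- **That specificity will be 0.56 and AN sensitivity 0.97.** That is the one-test, full-attendance case, not the stated design. If only 60% of positives attended and refusing negatives were replaced (one reading of the deferral rule), one-test specificity would be 1,743/(1,743 + 0.6 × 1,375.8) = 0.68.
- **That the likelihood ratios as printed carry this bias.** They are biased as defined in words (step 3: 0.968/0.441 = 2.19 against 8.09). The printed expressions each use one test row and are odds, which is a different error. The positive-row ones escape this bias; the negative-row one is touched only as single-test NPV is.

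A separate statistical analysis plan, not seen here, might contain a correction. That would not remove the point, because the protocol itself fixes both the formulas and the interval method.

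**Conclusion.** The point stands. The estimators in 7.1.1 and 7.1.3 and the intervals in 7.4 do not fit the sampling in 2.3 and 6.6.2. Specificity and accuracy are understated, AN/AA sensitivity is overstated, and single-test NPV is distorted. CRC sensitivity is biased upward by a smaller amount, and its exact interval may still cover the truth.

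The size is material under both readings of the third draw: miR-92a specificity is 8 to 22 points too low and combination specificity is in the range 0.52-0.68 against 0.81-0.86. These figures rest on the planning values in 5.5, the assumed FIT range, conditional independence of the tests and full attendance. The direction of the bias needs only that positives are scoped at a higher rate than negatives.

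**What to change.** Take all validly tested subjects as the frame. Estimate sensitivity, specificity, accuracy, NPV and the likelihood ratios as defined in words with inverse-probability-of-verification (Begg-Greenes) weights. The weight is one over the observed fraction scoped within miR-92a result × FIT result × age group × sex, with sparse cells collapsed. Report recorded selections and refusals per cell.

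For specificity, accuracy and AN/AA sensitivity, replace the exact binomial intervals with design-based or bootstrap ones. For CRC sensitivity, use an interval that stays valid with no or very few missed cancers: a Bayesian one, or one built from an exact upper limit on the CRC rate in scoped negatives. A bootstrap collapses to 100%-100% when no missed cancer is sampled. In the one-test case, no cancers among 1,756 scoped negatives gives an upper limit of 1 − 0.025^(1/1,756) = 0.0021, or about 26 missed cancers among 12,472, and a lower sensitivity limit near 38.4/64.6 = 0.59. State that precision will fall well short of 0.09. Label verified-only figures as unadjusted.

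The cost is revised wording and some programming on existing data. Section 1.5 has the analysis completed by December 2023, so this means re-analysis, and refusal counts can be used only if they were kept. The results will show wider intervals and a less favourable sensitivity, and selection through refusals may remain after weighting.
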